## 6.7 Safety Endpoint Analysis

Safety endpoint analysis will be determined based on adverse event data. The primary endpoint for safety is the incidence rate for each HF-OCT Imaging procedure related adverse event observed in the study. The overall rate and severity of adverse events will be analyzed and reported as a percentage based on the total number of catheters used for the HF-OCT procedures performed.

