The following sections describe the plans for statistical analysis of the evaluation results. The statistical analysis plan is based on the minimum enrollment into the Primary Analysis Population, which is 30 subjects.

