## 6.2 Sample Size Calculation

The study plans to enroll and image at least 30 subjects with the HF-OCT imaging technology, and up to 70 subjects. Conservatively, each participating subject is expected to have an average of 1.3 imaging pullbacks, for an anticipated total of approximately 39 imaging pullbacks (or more) captured with HF-OCT in the evaluation. The number of HF-OCT pullbacks performed in an eligible lesion is according to the discretion of the operator and in consideration of intravascular imaging guidelines. It is therefore expected that this evaluation will collect at least 39 HF-OCT pullback images. For the purpose of power calculation, we assume that 39 HF-OCT pullback images will be obtained from the minimum of 30 subjects. Another reasonable assumption to make in this case is that these 39 pullback images are statistically independent. The argument for statistical independence lies in the fact that CIL is very dependent on the details of the artery shape, the local flow, and the positioning of the guide catheter which delivers the flush. These factors yield a great deal of variability in the resulting CIL measurements even among vessels from the same subject.

The power analysis was performed using SAS/STAT PROC POWER and mean-based paired t-test, while the actual analysis will be median, or rank based due to abnormality in the skewed CIL data distribution. To compensate for the methodology difference, a Wilcoxon adjustment factor was applied. This adjustment factor to the sample size is based on an assumed data distribution. The adjusted sample size  $N_w$  is equal to:  $N_w = N_T / WW$ , where  $N_T$  is the unadjusted sample size using the paired t-test and  $WW$  is the Wilcoxon adjustment factor for the assumed data distribution and has a range between  $2/3$  and  $\pi/3$ . A conservative decision was made to use the adjustment factor resulting in the largest adjusted sample size  $N_w$ .

	Title: Vis-Rx Prime Micro-Imaging Catheter Clinical Evaluation Study – Clinical Investigation Plan	Document No. MISC-074
	Page 22 of 28	Revision: C

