The Gentuity HF-OCT technology is designed with a longer, 100 mm pullback length. It is expected that about 20% of the pullbacks will be in the 75 mm range. Setting the expected mean CIL at 45 mm and a target reference CIL of 35 mm (corresponding to an effect size 10 mm), standard deviation of 17 mm, 5% type 1 error rate, a study with 38 vessels will provide more than 80% power for the above hypothesis testing.

**Table 1:** Various effect size, standard deviation, and sample size to attain approximately 80% power.

Effect Size $\Delta = \mu - \mu_0$	SD in $\Delta$	Unadjusted Sample Size ( $N_T$ )	Adjusted Sample Size ( $N_w$ )	Power
6	10	24	36	80.4%
7	12	27	40	81.6%
8	14	27	40	81.5%
9	16	27	40	80.3%
10	17	25	38	80.6%
11	19	26	39	81.0%
12	21	27	40	81.5%

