### 6.3 Remarks About Statistical Analysis

All the analyses will be performed using SAS statistical software, version 9.4 or higher, primarily PROC FREQ for categorical data and PROC UNIVARIATE for continuous data. For categorical variables, subject counts and percentages will be generated. For continuous variables, mean, standard deviation, median and range will be generated. Two-sided p-values of less than 0.05 will be considered as statistically significant. Analyses will be based on the observed data only. Missing data will not be imputed. Multiple comparison adjustment will not be performed.

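### The primary safety endpoint is to be reported as counts and percentages with no measure of precision, although zero events would leave a rate of up to 11.6% possible at 30 subjects and 5.1% at 70

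*Combined protocol and SAP*

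**What the plan says.** Assessing safety is part of the study's stated purpose (Sections 1.1 and 5.4), and the data are meant to support a European submission (Sections 1.1 and 3). Section 6.7 opens with this sentence: "Safety endpoint analysis will be determined based on adverse event data". The endpoint itself is worded identically in Sections 5.3 and 6.7: "The primary endpoint for safety is the incidence rate for each HF-OCT Imaging procedure related adverse event observed in the study". For all events taken together, rate and severity are to be "reported as a percentage based on the total number of catheters used for the HF-OCT procedures performed".

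The general rule in Section 6.3 is: "For categorical variables, subject counts and percentages will be generated". Section 12 adds reporting by diagnosis term, severity and relatedness, tabulations of procedure-emergent and related events, and narratives for serious and related events.

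On size, Section 6.2 says: "The study plans to enroll and image at least 30 subjects with the HF-OCT imaging technology, and up to 70 subjects". Section 6.1 takes the lower end as the basis: "The statistical analysis plan is based on the minimum enrollment into the Primary Analysis Population, which is 30 subjects". The only justification offered for these numbers is the power calculation for CIL in Section 6.2.

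**The concern.** An incidence estimated from a few dozen subjects is imprecise, and for uncommon events the likeliest result is a count of zero or one. A percentage alone does not convey that imprecision. The plan gives no interval, no upper bound and no statement of the event rate that 30 to 70 subjects could miss.

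The other two endpoints are treated more fully. The technical endpoint has a threshold, an exact test and a decision rule (Section 6.6). Clinical performance has a target mean, a standard deviation and an explicit statement that no inference will be made (Section 6.5). Safety has none of these and no acknowledgement of the limit. What is at stake is how the safety result can be read in a regulatory file: a low percentage could reflect a low true rate or simply few subjects, and nothing pre-specified in the report would say how far the second explanation extends.

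**Working it through.** **Inputs from the plan.** Minimum 30 and maximum 70 imaged subjects (Section 6.2); 30 as the basis of the analysis plan (Section 6.1). The two-sided 95% level follows the plan's own convention in Section 6.3: "Two-sided p-values of less than 0.05 will be considered as statistically significant".

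**Assumption.** The plan divides by catheters but gives no expected number of catheters. The figures below take one analysis unit per subject.

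**The plan's own figure.** Section 6.2 sets this case: "Setting the expected mean CIL at 45 mm and a target reference CIL of 35 mm (corresponding to an effect size 10 mm"), with a standard deviation of 17 mm and 5% type I error. The exact power of a two-sided one-sample t-test with 25 observations is 80.56% (stated: 80.6%). Dividing by the Wilcoxon factor 2/3 gives 25 / (2/3) = 37.5, rounded up to 38 (stated: 38). The calculation reproduces and contains no safety quantity. The documents state no safety figure to reproduce.

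**Upper limit with zero events.** The exact (Clopper-Pearson) upper limit for 0 out of n is 1 − 0.025^(1/n) for a two-sided 95% interval and 1 − 0.05^(1/n) for a one-sided 95% bound.

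| n | two-sided 95% | one-sided 95% |
|---|---|---|
| 30 | 1 − 0.025^(1/30) = 11.6% (about 1 in 8.6) | 1 − 0.05^(1/30) = 9.5% (about 1 in 10.5) |
| 70 | 1 − 0.025^(1/70) = 5.1% (about 1 in 19.5) | 1 − 0.05^(1/70) = 4.2% (about 1 in 23.9) |

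The result at 30 does not depend much on the method: the Wilson upper limit is 11.4% and the rule of three gives 3/30 = 10.0%.

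**One event.** The exact two-sided 95% interval is 0.08% to 17.2% for 1/30 and 0.04% to 7.7% for 1/70.

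**Chance of seeing nothing.** The documents give no expected event rate, so 3% and 5% are illustrative assumptions. With 30 subjects, the probability of zero events is 0.97^30 = 40% at a true rate of 3% and 0.95^30 = 21% at 5%. With 70 subjects it is 0.97^70 = 12% and 0.95^70 = 3%.

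**Unit of analysis.** Section 6.3 counts subjects, while Section 6.7 divides by catheters. A subject may need more than one catheter, and an event may recur. Events per catheter are then not independent yes/no outcomes, and a binomial interval on that ratio could be falsely narrow. The proportion of imaged subjects with at least one event does fit the binomial model.

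**The case against.** The strongest reply is that the safety endpoint is descriptive. The plan sets no safety hypothesis, threshold or pass rule; the formal claim rests on CIL, and sizing a small study on its one tested endpoint is ordinary practice. Counts will accompany the percentages, and Section 12 adds tabulations and narratives, so a reader who sees 0 out of 30 can work out the interval. Section 6.3 does not forbid intervals. The plan also describes the catheter as similar to a cleared predecessor, with no anticipated change in complications (Section 1.2).

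Most of this stands. A reader might infer that the plan would treat 0% as proof of safety. The documents do not support that: no rule links any percentage to a safety verdict. A reader might also take one in nine as the rate the study leaves open. That figure needs zero events, minimum enrolment, a two-sided limit and one catheter per subject together; at 70 subjects the limit is about 1 in 19.5.

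The reply does not remove the need for an interval. An interval is itself descriptive and needs no hypothesis or extra patients. Fixing its method and unit in advance matters here because the plan's stated denominator is unsuited to the calculation a reader would make.

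**Conclusion.** The point holds as a limited reporting weakness. The named primary safety endpoint carries no measure of precision, and the sample size was never related to safety. With zero events, the exact two-sided 95% upper limit lies between 11.6% (30 subjects) and 5.1% (70 subjects), or between 9.5% and 4.2% one-sided, assuming one analysis unit per subject.

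The omission does not invalidate the study or alter a conclusion that the plan commits to drawing. The information is not lost either, since the counts will be reported; it is simply not pre-specified in a form that shows what the study can exclude. The change is worth making because it is cheap and bounds the safety statement.

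**What to change.** **Section 6.7.** Keep the per-catheter percentage. Beside it, report the proportion of imaged subjects with at least one event, for each related adverse event, for any related adverse event and for any serious adverse event. Give each proportion an exact (Clopper-Pearson) two-sided 95% confidence interval, including when no event is observed, and quote the upper limit in the safety conclusion. State that binomial limits will not be applied to event counts per catheter, because catheters may cluster within subjects and events may recur.

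**Section 6.2.** State that with zero events the two-sided 95% upper limit is 11.6% at 30 subjects and 5.1% at 70.

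**Cost.** A few sentences and slightly more output from PROC FREQ, which Section 6.3 already plans to use. The program should be checked to confirm that it returns a limit when no subject has the event. No new patients or data are needed. The downside is a less favourable safety statement.

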## 6.8 Procedural Error and Device Malfunctions

It is possible that a procedural error may occur that will lead to a pullback image being captured that has no or only partial clear imaging. For example, the injector pump (if used) had insufficient contrast media to clear the vessel, the bedside manifold was set such that delivered contrast media was not directed into the guide catheter and vessel, or the guide catheter became mis-aligned with the target artery prior to flush delivery. If such errors occur, they will be noted in the Case Report Form, the HF-OCT pullback will be repeated (at the operator’s discretion), and the pullback with the procedural error will not be included in the statistical analysis. Any procedural errors will be described in the final report.

The investigational device malfunctions will be recorded and detailed on the Device Malfunction Case Report Form. Document malfunctions that occur at setup and during use of the device will be collected.

	Title: Vis-Rx Prime Micro-Imaging Catheter Clinical Evaluation Study – Clinical Investigation Plan	Document No. MISC-074
	Page 24 of 28	Revision: C

## 7 Data Management

The collection and handling of subject clinical data will comply with regulatory guidelines and the Sponsor's Standard Operating Procedures (SOPs). All steps and actions taken regarding data management and quality assurance will be documented in the Sponsor's SOPs and data management plan.

Subject demographic, medical history, PCI details, and the Likert-scale performance evaluation will be collected via paper Case Report Forms (CRFs). The clinical data will be reviewed and approved by the clinical operator following the PCI and performance evaluation interview. The CRFs will collect only de-identified information. The data will be identified using methods to ensure HIPAA compliance (e.g., study participant ID). Following the PCI, clinical performance evaluation, and completion and approval of the CRFs, the collected data, including HF-OCT and coronary angiography images, will be transferred to Gentuity for data monitoring and clinical performance analysis.

HF-OCT images will be exported from the Gentuity HF-HF-OCT Imaging System Console in an anonymized format onto a USB drive. The anonymized HF-OCT image files will be transferred in a 21 CFR Part 11 compliant manner from the participating center to the core lab for later CIL image analysis. In addition, Gentuity will collect an anonymized copy of the pullback images. The CIL technical performance results will be entered into a CRF by the core lab and provided to the statistician for technical performance results analysis.

Centers and the core lab are responsible for retaining the primary data and records for this evaluation for a period of two years following the close-out of the study. The Sponsor should be contacted prior to the destruction of any records pertaining to this evaluation to ensure that they no longer need to be retained.

## 8 Amendments to the Evaluation

Amendments to this clinical evaluation protocol will be identified by protocol number and revision letter. All amendments will be accompanied by an addition to the revision history table on the cover page that identifies all substantial changes. The protocol reference number and revision letter will be placed on the title page and every subsequent page of an amendment.

A protocol amendment will not be implemented for enrollment of subjects before all necessary reviews and approvals have been obtained, including Sponsor approvals, clinical operator signatures, and local Institutional Review Board (IRB) approvals, as applicable.

## 9 Deviations from the Evaluation Protocol

Deviations to the informed consent process, inclusion or exclusion criteria, and evaluation procedures including the HF-OCT imaging and clinical performance evaluation will be identified and tracked to determine the potential impact on the evaluation results.

Deviations relating to subject informed consent and deviations resulting in safety events for the subject will be reported to the local IRB per their reporting policies.

	Title: Vis-Rx Prime Micro-Imaging Catheter Clinical Evaluation Study – Clinical Investigation Plan	Document No. MISC-074
	Page 25 of 28	Revision: C

## 10 Statements of Compliance

This evaluation will be conducted in compliance with international ethical and scientific quality standards, known as Good Clinical Practice (GCP), which includes review and approval by independent Institutional Review Boards (IRBs) before enrolling subjects, continuing review by IRBs, and obtaining and documenting informed consent of subjects prior to participation.

The study was designed to reflect GCP as outlined in International Organization for Standardization (ISO) 14155:2011. It will also be conducted in compliance with applicable local and national regulations, including FDA regulations (21 CFR Parts 11, 50, 54, and 56). It will furthermore be conducted in compliance with the International Council for Harmonization (ICH) Guideline E6 for GCP.

This clinical evaluation shall not begin until the required approvals are obtained from the applicable IRBs.

Subjects will not be paid to participate in the clinical evaluation. It is not expected that subjects will incur any additional cost due to their participation in the evaluation.

## 11 Informed Consent Process

Informed consent must be obtained in accordance with FDA regulations 21 CFR Part 50, 45 CFR Part 46, and ICH E6 Good Clinical Practice (GCP).

Each subject must sign and date the current version of the Informed Consent Form (ICF) as approved by the IRB prior to screening and enrollment in the evaluation. The subject will be provided with ample time and opportunity to ask about the details of the Gentuity HF-OCT devices and evaluation procedures in order to decide on whether to participate before informed consent is obtained. Coercion or undue influence of a subject for participation must be avoided and a subject's legal rights must not be waived.

An ICF will be provided to each prospective subject to include: an explanation of the evaluation; the expected benefits, risks, or inconveniences to them; an explanation of alternatives; Gentuity representative attendance of their PCI; provision of anonymized HF-OCT images to the Sponsor and core lab; and collection of de-identified clinical data. The ICF will contain non-technical language. Informed consent will be documented by the dated signatures of the subject and the individual obtaining informed consent. The clinical operator or designee will be responsible for obtaining informed consent.

## 12 Adverse Events

An Adverse Event (AE) is any untoward medical occurrence, unintended disease or injury, or untoward clinical signs (including abnormal laboratory findings) in a clinical evaluation subject, users, or other persons, whether or not related to the evaluation device. An AE would be any unfavorable or unintended sign, symptom, or disease that appears or worsens during the subject's participation in this evaluation.

Subject safety will be monitored throughout a subject's participation in the evaluation, from the beginning of the HF-OCT imaging procedure when the Vis-Rx Prime Catheter is inserted into the hemostatic valve, and continuing through their exit from the evaluation at the conclusion of the PCI

	Title: Vis-Rx Prime Micro-Imaging Catheter Clinical Evaluation Study – Clinical Investigation Plan	Document No. MISC-074
	Page 26 of 28	Revision: C

procedure. Any Adverse Events will be assessed by the clinical operator according to their relatedness to the Gentuity HF-OCT imaging procedure, Vis-Rx Prime Micro-Imaging Catheter, or HF-OCT Imaging System.

Any observed AE will be documented on the Adverse Event CRF. Any AE deemed to be possibly, probably, or definitely related to the Gentuity HF-OCT procedure, Vis-Rx Prime Catheter, or Imaging System will be reported to the IRB and evaluated as a complaint by Gentuity per Gentuity's complaint handling process. Non-related AEs will be tracked until the subject exits the evaluation at the conclusion of their PCI. Related AEs will be tracked until they are resolved.

Each AE will be classified as either non-serious or serious. A Serious Adverse Event (SAE) is defined to be an AE that:

- Led to death.
- Led to serious deterioration in the health of the subject, that either resulted in:
  - A life-threatening illness or injury, or
  - A permanent impairment of a body structure or a body function, or
  - In-patient or prolonged hospitalization, or
  - Medical or surgical intervention to prevent life-threatening illness or injury or permanent impairment to a body structure or a body function.
- Led to fetal distress, fetal death, or a congenital abnormality or birth defect.

Each AE will furthermore be classified as either anticipated or unanticipated. The anticipated AEs are listed in the Instructions for Use. Any unanticipated AEs will be further considered to determine if they may be an Unanticipated Serious Adverse Device Effect (USADE), which is defined to be a serious adverse device effect which by its nature, incidence, severity, or outcome has not been identified in the current version of the risk analysis report.

Adverse events will be reported by diagnosis term, severity, and relatedness to the HF-OCT imaging procedure, Vis-Rx Prime Catheter, and HF-OCT Imaging System. Narratives will describe serious events and related events. Tabulation of procedure-emergent adverse events will be generated and stratified by diagnosis term. Similar tabulations will be generated for procedure or device related AEs that are classified as definitely, probably, or possibly related to the evaluation procedure or products.

	Title: Vis-Rx Prime Micro-Imaging Catheter Clinical Evaluation Study – Clinical Investigation Plan	Document No. MISC-074
	Page 27 of 28	Revision: C

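### Tracking of adverse events judged non-related ends with the PCI, before some outcome-based seriousness criteria can be known, and no later reassessment of seriousness or relatedness is specified

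*Combined protocol and SAP*

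**What the plan says.** Section 12 (Adverse Events) sets the rules that matter here.

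- **Who judges.** "Any Adverse Events will be assessed by the clinical operator according to their relatedness to the Gentuity HF-OCT imaging procedure", and likewise to the catheter and the imaging system. No independent adjudication is described.
- **How long an event is followed.** This depends on that judgment. "Related AEs will be tracked until they are resolved". For the rest, "Non-related AEs will be tracked until the subject exits the evaluation at the conclusion of their PCI".
- **Seriousness.** "Each AE will be classified as either non-serious or serious". No time is given for making the classification. Several of the listed criteria are outcomes of the event.
- **What uses seriousness.** Section 12 promises narratives for serious events and for related events.

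Other sections describe what happens after the procedure. Section 5.6.6 exits the subject when the PCI is complete, with no follow-up; Section 5.6.3 and the synopsis (Section 1.4) agree. Section 7 has the operator review and approve the clinical data after the PCI and the rating interview, without mentioning seriousness or relatedness. In the Section 13 schedule, as it reads in the available text, AE assessment is marked only in the intra-procedure column, whereas device malfunction is marked both during and after the procedure.

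**The concern.** For AEs judged non-related, the plan requires a classification and stops collecting the information on which part of it depends. Take an event that begins during the case and that the operator attributes entirely to stenting. If it leads to a longer stay, or to death the next day, no planned step records this. Followed to the letter, the plan leaves the event as non-serious, and no narrative is written unless it qualified as serious on other grounds.

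There is also an asymmetry. A related event is followed to resolution, so later facts can support or weaken the label. For a non-related event no later facts are sought, so nothing in the plan would prompt a second look. The label is set by an unblinded operator who also rates the device (Section 5.1). Attribution can be difficult, because imaging and stenting take place in the same vessel and session, and pullbacks may be made both before and after the intervention (Section 5.2).

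At stake is the completeness of the serious-event record in a small single-arm study meant to support a European submission (Sections 1.1 and 3).

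**Working it through.** The documents state no figure on this point, so there is none to reproduce. The check sets the rules side by side; the arithmetic only gives scale.

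**Step 1. Can each seriousness criterion be established by the end of the PCI?** The criteria are those of Section 12; the right-hand column is my reading.

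| Criterion | Known when the PCI ends? |
|---|---|
| Death | Only if it occurs during the case |
| "A life-threatening illness or injury, or" | Usually yes |
| "A permanent impairment of a body structure or a body function, or" | Generally no; permanence needs time |
| "In-patient or prolonged hospitalization, or" | Generally no; length of stay is settled at discharge |
| Intervention to prevent a life-threatening or permanent outcome | Yes if done during the case; no if done later |

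The criterion on fetal outcomes is left aside. Two of these five generally cannot be established by then (permanent impairment, hospitalization), and two only in part (death, intervention).

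**Step 2. Does any other section supply the missing information for a non-related AE?**

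- Section 5.6.6: no, there is no follow-up after exit.
- Section 7: the operator's approval follows the PCI, but no reassessment and no discharge look-up is described.
- Section 13: AE assessment has no post-procedure mark.
- Section 12: follow-up past exit is provided for related AEs only.

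**Step 3. Which outputs are affected?** The narratives for serious events depend directly on seriousness. Section 6.7 does not: "The overall rate and severity of adverse events will be analyzed and reported as a percentage", and severity there need not mean the serious/non-serious class, since Section 12 treats the two as separate attributes. The primary safety endpoint in the same section counts imaging-related events and does not use seriousness.

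**Step 4. Scale.** Inputs: 30 to 70 imaged subjects (Section 5.6.5). Section 6.7 takes catheters used as the denominator, but the plan gives no catheter count, so I assume one per subject; with more catheters the percentages fall.

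- One event as a share, 1/n: 1/30 = 3.3%; 1/70 = 1.4%.
- Exact (Clopper-Pearson) two-sided 95% upper limit with 0 events, 1 − 0.025^(1/n): 11.6% at n = 30; 5.1% at n = 70.
- The same limit with 1 event, the 0.975 quantile of Beta(2, n − 1): 17.2% at n = 30; 7.7% at n = 70.

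Recording no serious event instead of one would thus lower the upper limit from 17.2% to 11.6% at 30 subjects, or from 7.7% to 5.1% at 70. The plan specifies neither a serious-event rate as an endpoint nor an interval for it. These figures show how much a single event weighs in a study of this size; they do not estimate how often misclassification would occur.

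**The case against.** Several stronger readings are tempting, and the documents do not support them.

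- **That the event is lost.** It is not. Every observed AE goes on the AE form whatever its attribution, and procedure-emergent AEs are tabulated by diagnosis. Only the tracking ends.
- **That the first attribution is final.** This would be inferred from silence. Section 12 sets no time for the judgment and does not forbid revision, and Section 7 gives the operator a review after the PCI, though not one directed at relatedness.
- **That no seriousness criterion can be known in time.** Life-threatening events, interventions during the case and deaths during the case can be recognised before exit, so many serious intra-procedural events would be caught.
- **That the primary safety endpoint is biased downward.** A later death or longer stay changes seriousness, not necessarily causation. A missed reclassification to related is possible, but nothing in the documents shows that it would happen or how often.
- **That ambiguous events escape.** Section 12 groups possibly related events with the related ones for reporting and tabulation, so on the natural reading they are also tracked to resolution. Vessel injury seen after both a pullback and stenting would often fall there. The gap is confined to events for which the operator rules out even a possible link.

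All five objections stand, and together they narrow the point. None answers the core of it: for events judged non-related, a classification is required, part of its basis is not collected, and no later check is described.

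**Conclusion.** The point holds in a limited form. For AEs judged non-related, the tracking rule in Section 12 stops before some of that section's own seriousness criteria can be assessed, and Sections 5.6.6, 7 and 13 do not close the gap. This is a stated rule that can give a wrong classification when followed, not merely a missing detail. Serious events judged non-related may stay recorded as non-serious and miss their narratives.

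Misclassification is a risk, not a certainty, and the documents do not allow it to be sized. The percentages above rest on one catheter per subject. The conclusion also rests on the schedule's AE mark being intra-procedure only, as the available text shows it. A post-procedure mark would soften the point without settling it, since the tracking sentence would still end at the PCI. The change should be made, but the point does not undermine the safety endpoint as defined.

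**What to change.** Leave the sentence on related AEs as it is, so that those unresolved at discharge keep their follow-up. Replace only the sentence on non-related AEs, for example with:

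> AEs judged non-related with onset in the collection window will be tracked until they resolve or until discharge from the index hospital stay, using the hospital chart; seriousness and relatedness are confirmed at that point, any change of attribution is reported, and an AE reclassified as related is then tracked until resolved.

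The onset window does not change. Bring the follow-up row of the synopsis (Section 1.4), Sections 5.6.3 and 5.6.6, the Section 13 schedule and the consent text into line. The exit wording already sits uneasily with following related AEs to resolution, so both can be settled together.

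The cost is a chart look-up for the few subjects with an AE, space on the AE form for the confirmed classification, and an amendment with the approvals that Section 8 requires. No visit or procedure is added. Data collection would run past the stated exit, and some events may move to serious or related. One limit remains: permanent impairment may still be unknown at discharge.
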